## Rational

The clavicle stands out as one of the most distinctive long bones, possessing various notable characteristics in its structure and shape that render it susceptible to fractures. Fractures of the clavicle rank high among the most common bone injuries, comprising 2-5% of all adult fracture, and therefore, are among the most frequent fractures seen in orthopedic practice.

Previous epidemiologic studies indicate that clavicle fractures account for up to 5% of all adult fractures and up to 44% of all shoulder girdle fractures. Distal third fractures (DCFs) account for 15-20% of all clavicle fractures and are observed in both young people with high velocity trauma and the elderly due to falls (bimodal distribution).

Furthermore, DCFs are classified according to Neer classification system, into five types depending on the position of the fracture line relative to the coracoclavicular (CC) ligament. Among these, type II and type V fractures represent unstable distal clavicle fractures (UDCFs), characterized by considerable displacement resulting from the separation of the coracoclavicular ligament from the proximal fragment. Specifically, Type 2 indicates that the fracture is immediately medial to the coracoclavicular ligaments or between the two ligaments, with one ruptured, but do not involve the acromioclavicular (AC) joint.

As such, it was found that non-operative treatment of an unstable distal clavicle fracture (Neer 2) results in a high disunion rate of up to 33%, and subsequently, surgical therapy is often recommended.

Several approaches have been proposed including anterior and bra-strap approaches, with trans- or extra-articular (k-wire) fixation being the most prevalent, although this involves a high risk of problems, including pain migration and loss of reduction. Moreover, it was found that Plate fixation is precarious because the distal fragment is often tiny and the metaphyseal bone is soft. As a result, a hooked plate with an extension under the acromion has been designed to provide more robust attachment. However, the main concern is subacromial impingement or rotator cuff damage.

In this regard, while significant research has been conducted on clavicle fractures and their treatment options, no definitive guidelines or optimal approach have been

established. Hence, the aim of this study was to analyze and compare the clinical and radiological results between the two surgical technique, the Tension Band Wiring (TBW) and Hook plate ones, and evaluate the functional outcomes of surgical treatment in displaced, closed, and isolated distal clavicle fractures in adults.

## **Material and methods**

This study is a comparative retrospective study of 38 patients who had unstable distal clavicle fracture (Neer 2) featured in Figure 1. treated either with TBW technique (Figure 3 and 4) or A.O Hook plate fixation (Figure 2), and presented to the orthopedic department of Tishreen University Hospital, in Lattakia, Syria, between August 30, 2019 and August 30, 2022.

Data was extracted from the medical records of patients in the form of case sheets, discharge cards, x-rays, etc. The type of fracture was determined by Neer's classification.

We included patients who met the following criteria: Patients with unstable distal third clavicle fracture (Neer type 2), aged between 18 and 65 years old. Nevertheless, Patient who had open fractures, pathological fractures, fractures associated with brachial plexus or pulmonary or vascular injury, acromioclavicular joint disruption, and musculoskeletal disease that affects the joint, were excluded.

Preoperative shoulder x-rays in AP with (10-15) ° cephalic tilt (ZANCA View) and axillary view were taken. In addition, Basic lab tests were done for all patients on admission. We used A.O Hook plate with (4-7) holes, (3.5) mm screws and (12.15.18) mm of hook depth, and 2 Kirschner-wires of (2.0) mm and stainless steel wire of (18) gauge in the TBW technique.

Specified postoperative protocol was followed for all patients contained:

1. Arm immobilization with a sling inside the operation room under anesthesia.
2. I.V antibiotics and analgesic
3. A sterile wound dressing was applied routinely.

The surgical stitches were removed after (10-14) days after surgery, and all patients were subjected to the rehabilitation and physical treatment.

One examiner measured the outcome based on Constant-Murley score at 1.5-, 3-, 6-, 9-, and 12- month intervals. In this system, both subjective and objective clinical data are included, with a maximum score of 100 points, as the following: Pain (15 points), activities of daily living (20 points), range of motion of the shoulder (40 points), and muscle power (25 points) were evaluated.

Furthermore, Radiological assessment was performed immediately after surgery, followed by evaluations at 3, 6, 12, and 24-week intervals to monitor healing progress and implant positioning. Recorded complications included infection, non-union, mal-union, pin migration, hardware impingement, and stiffness. The final outcome was assessed based on union status, time to fracture union, shoulder joint range of motion, ability to perform daily activities, and return to pre-injury status.

In the TBW group: The fixation method involved trans-articular fixation through the acromioclavicular joint, supplemented with an additional cerclage wire tension band for enhanced stability. Following surgery, the operated shoulder was supported with a triangular sling for a period of 4 to 6 weeks. Gentle mobilization was permitted once pain subsided, although full range of motion was limited due to pin impingement until implant removal.

In the Hook plate group: The operative procedure, as outlined in prior studies, involved creating a tunnel in the sub-acromial space posterior to the acromioclavicular joint and inserting the hook into this tunnel. If necessary, the plate was contoured to match the clavicle's shape, with careful consideration given to the appropriate depth of the hook. Dynamic compression was utilized to secure the plate in place. Following surgery, the shoulder was supported with a triangular sling for a period ranging from 2 to 4 weeks. Mobilization commenced at the earliest opportunity, typically resulting in full range of motion within three to four weeks. It is worth mentioning that across both groups, heavy manual labor was prohibited until evidence of solid fracture union was observed.

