## Statistical analysis

The Student's t-test, chi-square test with Yates' correction, Fisher's exact test, and Friedman test were used to compare the two groups. The statistic software SPSS 10.0 (SPSS, Inc., Chicago, IL) was used to analyze the data; p values below 0.05 were considered significant.

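### The retrospective TBW versus hook-plate comparison states no method of choosing technique and plans only unadjusted tests, so any prognostic factor that differs between groups would be mixed with technique

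*Combined protocol and SAP*

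**What the plan says.** The Rational section gives the purpose: "the aim of this study was to analyze and compare the clinical and radiological results between the two surgical technique". Just before that it notes that "no definitive guidelines or optimal approach have been" established, so no external rule is cited that would have fixed the choice of operation.

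Material and methods describes the design ("This study is a comparative retrospective study of 38 patients who had unstable distal clavicle fracture (Neer 2"), with patients "treated either with TBW technique (Figure 3 and 4) or A.O Hook plate fixation (Figure 2". The source is existing records: "Data was extracted from the medical records of patients in the form of case sheets, discharge cards, x-rays". Group sizes, the reason for choosing a technique, randomisation and matching are not mentioned in the available text. Confounding is limited only by restriction: Neer type 2 fractures, patients "aged between 18 and 65 years old", and a list of exclusions.

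The Statistical analysis section is two sentences long. It names Student's t-test, Yates-corrected chi-square, Fisher's exact test and the Friedman test, with significance at p below 0.05. It says that these, including the "Friedman test were used to compare the two groups". No regression, stratification, matching or propensity method appears there or elsewhere. The section does not say which variables each test is for, or whether baseline characteristics are compared.

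**The concern.** In a retrospective comparison the groups are formed by whatever led to one operation rather than the other. If that is related to prognosis, the raw difference between groups is partly a difference between patients. A p-value below 0.05 then no longer carries a 5% error rate for an effect of technique. If nothing prognostic differs systematically, a single t-test, chi-square or Fisher comparison keeps its usual interpretation. The plan does not let a reader tell which case applies.

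Age is a natural example. The Rational section describes distal-third fractures as "observed in both young people with high velocity trauma and the elderly due to falls (bimodal distribution", and the eligibility limits still span 65 − 18 = 47 years. Range of motion and muscle power make up 40 + 25 = 65 of the 100 Constant-Murley points, and age could plausibly act through both. That is a reason to look at age. It is not evidence that the groups differ in age.

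The Friedman test is a separate difficulty. It compares repeated measurements within patients, so it neither compares two independent groups nor adjusts for anything that differs between them.

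**Working it through.** **No plan figure to reproduce.** The documents give no group sizes, SD, effect size or power; 38 is a count of records. What follows is illustration only.

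**Inputs.** From the documents: 38 patients, age limits 18 to 65, a 100-point score, threshold 0.05 (taken as two-sided). Assumed: 19 per arm, no true technique effect, SD 10 points, score falling 0.2 to 0.5 points per year of age.

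**Step 1: bias and rejection with a fixed age gap.** Bias = slope × age gap. With total SD 10, the standard error is 10 × √(2/19) = 3.24. The rejection rate comes from the noncentral t distribution with 36 degrees of freedom and noncentrality bias/3.24.

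| Slope | Gap (years) | Bias | Noncentrality | Rejection |
|---|---|---|---|---|
| 0.2 | 5 | 1.0 | 0.31 | 6.0% |
| 0.5 | 5 | 2.5 | 0.77 | 11.7% |
| 0.2 | 10 | 2.0 | 0.62 | 9.2% |
| 0.5 | 10 | 5.0 | 1.54 | 32.3% |

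**Step 2: respecting the age limits.** Truncation at 18 and 65 shrinks the gap, and age variation within arms adds to the residual SD of 10. Each row is 20,000 simulated trials, t-test against a linear model with group and age. Single-peaked age is normal with mean 38 and SD 12, truncated, with one arm shifted. Two-peaked age mixes N(28, 7) and N(55, 7), truncated, with different older shares by arm.

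| Age model | Slope | Gap | Bias | Unadjusted | Age-adjusted |
|---|---|---|---|---|---|
| Single peak, shift 5 | 0.2 | 3.75 | 0.77 | 5.5% | 4.8% |
| Single peak, shift 10 | 0.3 | 7.4 | 2.24 | 9.8% | 5.0% |
| Single peak, shift 10 | 0.5 | 7.43 | 3.76 | 16.9% | 4.9% |
| Two peaks, 40% vs 60% older | 0.2 | 4.9 | 1.03 | 6.1% | 5.0% |
| Two peaks, 40% vs 60% older | 0.5 | 4.9 | 2.47 | 9.7% | 5.1% |
| Two peaks, 35% vs 65% older | 0.5 | 7.5 | 3.71 | 15.5% | 4.9% |

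Across all cells, including single-peak means of 35 and 40, bias runs from 0.7 to 3.8 points and unadjusted rejection from 5.4% to 17%. At slopes of 0.2 to 0.3 rejection is at most about 10%. With slope 0, or with no shift, it is 4.6% to 5.5%, so an age gap alone does no harm unless age is prognostic.

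**Step 3: what age adjustment does not do.** The adjusted column sits near 5% because age is the only confounder simulated. Add an unmeasured 4-point group difference at slope 0.5:

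- No age gap: rejection goes from 18.8% to 21.8% with adjustment (single peak) and from 16.5% to 22.0% (two peaks).
- A 7.4-year gap with the unmeasured difference in the opposite direction: the two biases nearly cancel, about 3.7 against 4 points. Rejection is 5.0% unadjusted and 19.7% adjusted.

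**Step 4: a balance test would not settle it.** At 19 per group, the power to detect a 5-year age difference is 20% to 34% (age SD 14 down to 10). For a 10-year difference it is 60% to 87%.

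**Step 5: precision.** 95% confidence-interval half-width, unadjusted to adjusted:

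- Single peak, no gap, slope 0.5: 7.36 to 6.63 (−0.7).
- Single peak, gap 7.4, slope 0.2: 6.67 to 7.09 (+0.4).
- Single peak, gap 7.4, slope 0: 6.52 to 7.07 (+0.55, the cost when age is not prognostic).
- Two peaks, no gap, slope 0.5: 7.95 to 6.63 (−1.3).

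**The case against.** The strongest reply is that both links needed for confounding by age are supplied from outside the documents. The bimodal remark is background on distal-third fractures in general, not on this cohort, and the limit at 65 removes part of the older peak. Nothing in the text links age to the choice of technique, or age to the Constant-Murley score. The numbers depend on the assumptions: the low end of Step 2 cannot be told apart from 5%, and the 32.3% in Step 1 needs a fixed 10-year gap with the steepest slope. All of this stands.

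A reader might go further and infer that the groups do differ in age, or that bone quality or fragment size steered the choice, since the Rational section mentions small distal fragments and soft bone as a difficulty with plates. The documents do not support either inference: no baseline data by group are given, and that remark is not tied to how any patient here was treated. Nor does any age difference bias the result by itself, as the slope-0 results show.

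It is also fair to say that adjusting for age is a narrow remedy. The final outcome includes union status and time to union, complications are recorded too, and Step 3 shows that adjustment can make matters worse. That limits what the added model can claim, but does not remove the reason to report it.

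What the reply does not touch is the documented gap: no stated basis for choosing technique, and no adjusted analysis in a study whose aim is to compare techniques.

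**Conclusion.** The concern holds in conditional form. The comparison is retrospective, the available text does not say how technique was chosen, and every listed test is unadjusted. Any prognostic factor that differs between the groups would therefore be read as an effect of technique. The documents neither show nor exclude such an imbalance.

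The possible size rests wholly on assumed group sizes, SD, slope and age distribution, and ranges from negligible to a rejection rate roughly three times nominal (17% against 5%) in Step 2. The gap in the plan is well established; its consequence for this cohort is unknown. The 5% reference is for one comparison; the several outcomes and five score times raise a separate multiplicity question. It is a change the plan should make, not proof that the results are wrong.

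**What to change.** In Statistical analysis:

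- Keep the t-test, chi-square and Fisher tests as unadjusted comparisons, and say which variables each covers. Do not rely on the Friedman test for the comparison between groups.
- Add a supporting linear regression of the 12-month Constant-Murley score (the last listed assessment) on technique and age. Report its 95% confidence interval beside the unadjusted difference. This does not designate a primary endpoint.
- Show baseline characteristics by group with standardised differences.

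In Material and methods, state how technique was chosen. Word conclusions as association. Say that age adjustment removes only confounding by age, may move the estimate either way if unmeasured factors also differ, and leaves union and complication outcomes unadjusted.

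**Cost.** Age is an eligibility criterion, so the model needs no new data. It uses one degree of freedom in 38 patients. Under the assumed inputs the interval half-width may shrink, or may grow by up to about 0.6 points if age is not prognostic. The model takes the age effect as linear on a score capped at 100, so residuals need checking. The rest is wording and one table.

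### Loss of reduction and unplanned re-operation are not among the listed outcomes, so a fixation that failed early, was revised and then united could be missed in the comparison

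*Combined protocol and SAP*

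**What the plan says.** All of this is in the combined protocol and SAP.

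- **Rational.** The most common approach is described as k-wire fixation, "although this involves a high risk of problems, including pain migration and loss of reduction". No rate is given.
- **Material and methods, groups.** "This study is a comparative retrospective study of 38 patients", "treated either with TBW technique (Figure 3 and 4) or A.O Hook plate fixation (Figure 2". The number per group is not stated. Eligibility covers fracture type and age ("Patients with unstable distal third clavicle fracture (Neer type 2), aged between 18 and 65 years old") and a list of exclusions. Neither mentions earlier fixation of the same fracture or receipt of both implants.
- **Material and methods, data.** "Data was extracted from the medical records of patients in the form of case sheets, discharge cards, x-rays, etc".
- **Material and methods, films.** "Radiological assessment was performed immediately after surgery, followed by evaluations at 3, 6, 12, and 24-week intervals". Their stated purpose covers both healing and the position of the implant.
- **Material and methods, complications.** "Recorded complications included infection, non-union, mal-union, pin migration, hardware impingement, and stiffness".
- **Material and methods, final outcome.** Five items: whether the fracture united, how long that took, shoulder movement, daily function, and recovery to the state before injury.
- **Statistical analysis.** Tests, software and the 0.05 threshold, with no rule on how an event after a second operation is attributed.

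**The concern.** Failure of the fixation is one of the main ways in which two implants for the same fracture can differ. The plan itself names one form of it, loss of reduction, as a high risk of the technique family used in one group. It also collects the films that would show it. But the lists of what is compared have no place for it, and none for the re-operation that might follow.

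Take a patient whose reduction is lost in the first weeks, who is re-operated, and whose fracture then unites. Union status is favourable. Non-union and mal-union need not apply. Pin migration applies only if the wires moved. The complication comparison could then show nothing against the technique that failed, and would understate its failure rate. The same holds in either group, but the Rational section names loss of reduction only for k-wire fixation.

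**Working it through.** **1. Is there a figure to reproduce?** No. The documents give no event rate, group split or power calculation. The check is a comparison of the text, followed by an illustration on assumed counts.

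**2. Named risk against recorded items.**

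| Event | Named as a risk in Rational | Visible in planned data | Listed complication or final outcome |
|---|---|---|---|
| Migration (the text says pain, apparently meaning pin) | yes | x-rays | yes |
| Hook impingement | yes | clinical examination | yes |
| Loss of reduction / fixation failure | yes, for k-wires (loss of reduction) | x-rays at 3, 6, 12 and 24 weeks | **no** |
| Unplanned re-operation | not named | patient records | **no** |

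Loss of reduction is the one risk in this table that the plan names and does not carry into its lists.

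**3. What the remaining items would catch.** Mal-union or non-union catches a failure that is left alone or never heals. Pin migration catches one form of wire failure. Time to union catches a revised case only if the clock starts at the first operation, and the text says only surgery. Early functional scores may be lower in such a patient, but they do not identify a fixation failure.

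**4. Scale of an uncounted failure (assumed).** Suppose 19 patients per group, grouped by first fixation, with k early TBW failures that are revised and unite, and none in the hook-plate group. The true rate is k/19, and the listed items could show 0/19. For k against 0 with equal groups, the two-sided Fisher p is 2·C(19,k)/C(38,k):

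- k = 2: 2/19 = 10.5%, p = 2·171/703 = 0.49
- k = 3: 3/19 = 15.8%, p = 2·969/8436 = 0.23
- k = 4: 4/19 = 21.1%, p = 2·3876/73815 = 0.105
- k = 5: 5/19 = 26.3%, p = 2·11628/501942 = 0.046

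Small numbers of missed failures change the description of the results, not a significance test. Five would be needed at this split.

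**5. Why attribution should be stated once the event is recorded (assumed counts, two-sided Fisher exact).** One failed TBW patient is handled in four ways:

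| Handling | True 5 vs 0, split 19/19 | True 4 vs 0, split 16/22 |
|---|---|---|
| Kept with first fixation | 5/19 vs 0/19, p = 0.046 | 4/16 vs 0/22, p = 0.025 |
| Moved, failure credited to hook plate | 4/18 vs 1/20, p = 0.17 | 3/15 vs 1/23, p = 0.28 |
| Moved, failure uncounted | 4/18 vs 0/20, p = 0.041 | 3/15 vs 0/23, p = 0.054 |
| Dropped | 4/18 vs 0/19, p = 0.046 | 3/15 vs 0/22, p = 0.059 |

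At 19/19, moving the patient uncounted or dropping the patient barely changes p, while the TBW rate falls from 26.3% to 22.2%. With larger imbalances (7 vs 1 at 14/24) all four handlings stay below 0.05, at 0.002 to 0.011. These counts were chosen near the threshold and are not estimates.

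**The case against.** The strongest reply has four parts.

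**Grouping.** A reader might infer that, because no index operation is named, a patient converted from one implant to the other qualifies for either group, or is grouped by the final implant. The documents do not support that. The dates in Material and methods attach to presentation at the department, pre-operative films and admission tests are described, and each group is described through a single operation followed by follow-up. The natural reading is grouping by first fixation, and the either/or wording treats the groups as exclusive. This part of the reply stands. What remains is that a one-line statement would remove the doubt.

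**Recording.** A reader might also infer that such a failure is recorded nowhere. That is too strong. Films are scheduled at 3 and 6 weeks, three related complications are listed, and the verb used for the list (included) need not mean it is complete. This stands as partial mitigation. It does not give loss of reduction or re-operation a defined place in the comparison.

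**Occurrence.** No revised or dual-implant patient is reported. The Rational section speaks of k-wire fixation in general, and the TBW construct here adds a cerclage tension band for stability. Nothing says that lost reductions were revised, or revised to the other implant. This stands, and it is why no size can be given. But without a re-operation item, a reader of the results could not tell none from unrecorded.

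**Cost.** The study is retrospective with its patients already counted, so the change means going back to records. That is fair, but the films and records are already the stated data source.

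**Conclusion.** The concern holds as a gap in the outcome list. The plan names loss of reduction as a high risk of k-wire fixation and takes the films that would show it, but lists neither that event nor unplanned re-operation for comparison. A failure revised to union could be missed, with non-union, mal-union and pin migration a partial safeguard.

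The size is unknown. It depends on how many such patients exist among the 38, and the documents report none. The 10.5% figure and every p value above rest on assumed counts and splits. The two-failure example would not be significant even if fully recorded (p = 0.49), so the foreseeable harm is an understated failure rate, not a reversed test result. The documents do not show that patients were placed in the wrong group. This is a cheap improvement, not a flaw that invalidates the comparison.

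**What to change.** 1. Add two items to the compared complications: loss of reduction or fixation failure, and unplanned re-operation. Keep the second separate from planned implant removal, which the TBW description already anticipates and which would otherwise swamp it.
2. Extract both from the existing x-rays and operation records, using a definition of loss of reduction written down before the films are re-read.
3. State that each patient belongs to the group of the first fixation of that fracture and stays there, and that every event counts against that technique.
4. Report how many patients received both implants, even if the answer is none.

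This changes recording and analysis only. It costs a modest re-review of 38 charts, a few sentences of text, and possibly less favourable failure rates.

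### Time to union can be known only to within gaps of 3, 3, 6 and 12 weeks between scheduled films, so a t-test on mean weeks to union would misstate the size of the difference and lose power

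*Combined protocol and SAP*

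**What the plan says.** The aim, stated at the end of the Rational section, includes comparing radiological results between tension band wiring (TBW) and the hook plate. Under Material and methods, films are taken immediately after surgery, "followed by evaluations at 3, 6, 12, and 24-week intervals to monitor healing progress and implant positioning". The same section names the outcome: "The final outcome was assessed based on union status, time to fracture union, shoulder joint range of motion", among other items. It gives no definition of radiographic union and no rule for its date.

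The Statistical analysis section lists its methods together: "The Student's t-test, chi-square test with Yates' correction, Fisher's exact test, and Friedman test were used to compare the two groups". No test is tied to any outcome, and no method for times known only to within an interval is named.

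The study is a retrospective review of 38 patients. On sources, "Data was extracted from the medical records of patients in the form of case sheets, discharge cards, x-rays, etc". Constant-Murley visits follow a separate calendar of 1.5, 3, 6, 9 and 12 months.

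**The concern.** A film shows that union has happened by that day, not when it happened. On the stated schedule, the true date lies somewhere between the last film without union and the first film with it. The later gaps are wide: the one from 12 to 24 weeks is half of the radiographic follow-up.

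If the date of the first film showing union is used as the healing time, the outcome takes four unevenly spaced values, and a t-test treats them as exact. This is a different matter from how non-unions are counted, because it arises when every fracture unites. At stake are each arm's mean weeks to union, which a reader would take literally, the size of the difference between techniques, and the chance of detecting a real one.

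**Working it through.** The plan states no effect size, SD, power or sample size calculation, so it has no figure to reproduce.

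**Inputs from the document.** Films at 3, 6, 12 and 24 weeks; 38 patients; significance at 0.05.

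**Assumptions (not in the document).** Log-normal true times to union; SD 2, 3 or 4 weeks; arm means from 8 to 18 weeks; true difference 2 weeks; 19 patients per arm; two-sided test; union dated to the first scheduled film showing it; the few simulated times beyond 24 weeks counted at 24.

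**Step 1: the gaps.** 3 − 0 = 3, 6 − 3 = 3, 12 − 6 = 6 and 24 − 12 = 12 weeks, or 12.5%, 12.5%, 25% and 50% of 24 weeks. The clinical visits at 1.5, 3 and 6 months fall at about 6, 12 and 24 to 26 weeks, so they do not fill the last gap.

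**Step 2: single patients.** This needs only the dating assumption.
- Unions at 11 and 13 weeks (2 apart) are recorded as 12 and 24 (12 apart).
- Unions at 13 and 23 weeks (10 apart) are both recorded as 24.

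**Step 3: arm means.** For a true mean m and SD s, σ² = ln(1 + s²/m²) and μ = ln m − σ²/2. The share united by week w is Φ((ln w − μ)/σ). The recorded mean is 3p₁ + 6p₂ + 12p₃ + 24p₄, where the p are the shares first seen united at each film.

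Example, SD 2, means 11 v 13:
- Mean 11: 0.72 first seen at 12 weeks and 0.28 at 24, so 0.72 × 12 + 0.28 × 24 = 15.4.
- Mean 13: 0.33 and 0.67, so 0.33 × 12 + 0.67 × 24 = 20.0 (20.1 before rounding the shares).
- Recorded difference 4.7 weeks, for a true 2.

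**Step 4: the range.** Power is for Student's t-test, from 20,000 simulated trials; a dash means it was not computed.

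| SD | True means | Recorded means | Recorded difference | Power, true times | Power, film dates |
|---|---|---|---|---|---|
| 2 | 8 v 10 | 11.6 v 13.8 | 2.2 | 0.846 | 0.433 |
| 2 | 11 v 13 | 15.4 v 20.1 | 4.7 | – | – |
| 2 | 12 v 14 | 17.6 v 22.1 | 4.5 | 0.845 | 0.715 |
| 2 | 14 v 16 | 22.1 v 23.9 | 1.7 | 0.849 | 0.277 |
| 2 | 16 v 18 | 23.9 v 24.0 | 0.15 | – | – |
| 3 | 8 v 10 | 11.5 v 14.3 | 2.8 | 0.531 | 0.384 |
| 3 | 10 v 12 | 14.3 v 17.4 | 3.1 | 0.527 | 0.364 |
| 3 | 12 v 14 | 17.4 v 20.8 | 3.4 | 0.523 | 0.417 |
| 3 | 16 v 18 | 23.1 v 23.9 | 0.8 | – | – |
| 4 | 10 v 12 | 14.3 v 17.1 | 2.8 | 0.346 | 0.286 |
| 4 | 14 v 16 | 19.9 v 22.2 | 2.3 | 0.345 | 0.282 |

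Across the scenarios examined, recorded arm means are late by 3.4 weeks (SD 4, mean 8) to 8.1 weeks (SD 2, mean 14).

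**Step 5: no true difference.** With equal arm means of 8, 10, 12 or 14 weeks and a common schedule, the t-test on film dates rejects in 0.041 to 0.053 of trials.

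**The case against.** Four points can be made against this concern.

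**The premise is partly inferred.** The document lists film times but does not say that union was dated only from them. A chart review may hold unscheduled films, or union may have been dated clinically. Nor does the plan say that mean weeks were compared; chi-square or Fisher's exact test could be applied to the share united by a given film. This stands, so the finding is conditional. It does not remove the problem: a named final outcome has no dating rule, and the only listed test that fits a numeric time in two independent groups is the t-test.

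**A stronger reading is tempting.** A reader might infer that such a comparison reflects the film calendar more than healing. That is not shown. Over 18 scenarios (three SDs, six pairs of means from 8 v 10 to 16 v 18), the squared correlation between true and recorded time is at least 0.5 in 12. The expected direction is kept, and a shared calendar does not create a false difference.

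**A parametric interval-censored model is not a safe main remedy.** When only the 12- and 24-week films contain unions, location and spread are not separately identified. In 200 simulated trials at SD 2, 11 v 13, a log-normal fit averaged 1.1 weeks for a true 2.0, and 99% of trials had at most two distinct film dates. At SD 2, 16 v 18, the estimate ran from 0.5 to 3.2 weeks depending on the starting value. This stands, and the fix reflects it.

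**Most of the lost power cannot be recovered.** At SD 3, 10 v 12, a smaller run of 200 trials gave power 0.32 on film dates, 0.38 with the interval-censored model and 0.56 on true times. This also stands.

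**Conclusion.** The concern holds in conditional form. If union is dated to the first scheduled film showing it and mean weeks are compared by t-test, the arm means are about 3 to 8 weeks too late and a true 2-week difference is recorded as about 0.15 to 4.7 weeks. Power falls too, for example from 0.53 to 0.36 at SD 3, 10 v 12 weeks. None of this requires a single non-union.

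The gap arithmetic follows from the schedule alone, provided no other films exist. The sizes rest on the assumed distribution, means, SDs and equal split of 38 patients. The finding concerns the size of the estimate and the power, not false positives. If unscheduled films were taken more often in one arm, bias could arise, but the document gives no data on that. Time to union is one of several unranked outcomes, so this should be changed, but it does not undermine the whole comparison.

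**What to change.** 1. State how union and its date are defined. Do not report or compare mean weeks to union as exact times.
2. For each patient, extract two dates from the records: the last film without union and the first film with it. Use actual film dates and include unscheduled films.
3. As the main result, report the percentage united by the 6-, 12- and 24-week films in each arm, with the between-arm difference and its confidence interval.
4. Compare the arms with a test on the ordered film intervals, for example a discrete-time analysis or an interval-censored log-rank test.
5. Use a parametric interval-censored model only as a supplement, and only if at least three film intervals contain unions.
6. Say in the conclusion that union is known only to within the gap between films.

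**Cost.** Revised wording in the Statistical analysis section, two dates per patient (2 × 38 = 76) from films already on file, and a short script for a test not now listed. No new patients or films are needed.

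**Downsides.** The result is a percentage by film instead of a mean in weeks. A test at a single film has less power than one using the ordered intervals. Power lost to the wide spacing of films is largely not recoverable.
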